**Steroids (based on average steroid dose between visits):**

1. Percent of subjects with daily prednisone dose reduced to  $\leq 7.5$  mg/day from  $> 7.5$  mg/day at baseline by visit (DO=F).
2. Percent of subjects with daily prednisone dose increased to  $> 7.5$  mg/day from  $\leq 7.5$  mg/day at baseline by visit (LOCF).
3. Percent of subjects with any increase in steroid use by visit (all patients, LOCF).

4. Percent of subjects with a 50% decrease in steroid dose by visit (DO=F; in patients receiving steroids at baseline).
5. Percent of subjects with a 50% increase in steroid dose by a minimum  $\geq 5$  mg/day by visit (LOCF; in all patients).
6. Mean/median changes in steroid dose (mg/day) by visit.

#### **SLICC Damage Index (DI):**

1. Mean change from baseline in SLICC DI at Week 52.
2. Percent of patients with any SLICC DI worsening (change  $> 0$ ) at Week 52 compared with baseline.

#### **Patient Reported Outcome:**

1. Mean change in FACIT-fatigue score at Week 52 and by visit.
2. Percent of patients with improvement in FACIT-fatigue score exceeding the MCID ( $\geq 4$ ) by visit.

#### **Biological Markers:**

1. Median/mean percent change and median/mean absolute change from baseline in absolute B cell subsets (CD20 $^{+}$ , CD20 $^{+}$ /27 $^{+}$  memory, CD20 $^{+}$ /27 $^{-}$  naïve, CD20 $^{+}$ /69 $^{+}$  activated, CD20 $^{+}$ /138 $^{+}$  plasmacytoid, CD19 $^{+}$ /27 $^{\text{BRIGHT}}$ /38 $^{\text{BRIGHT}}$  SLE subset, CD19 $^{+}$ /CD24 $^{\text{HIGH}}$ /CD38 $^{\text{HIGH}}$  regulatory B cell, and CD20 $^{-}$ /138 $^{+}$  plasma cells) by visit. Only in regions/countries where assessment of B cells is feasible.
2. Median/mean percent change and median/mean absolute change from baseline by visit
  - Total serum immunoglobulin (IgG and other isotypes: IgM and IgA).
  - Autoantibodies\* (anti-dsDNA, ANA, anti-phospholipid antibodies [aCL, lupus anticoagulant,  $\pm$ beta-2-glycoprotein-1], and extractable nuclear antigens [ENAs]).
  - Complement (C3, C4) levels.
3. Percent of patients with normalized serological activity at Week 52 and by visit
  - IgG, IgM and IgA (high to normal/low).
  - Autoantibodies\* (anti-dsDNA, ANA, anti-phospholipid antibodies [aCL, lupus anticoagulant,  $\pm$ beta-2-glycoprotein-1], and extractable nuclear antigens [ENAs]) present to absent.
  - Complement (C3, C4, and C3 AND C4) levels low to normal/high.

\*Anti-dsDNA will be collected monthly throughout the study for SELENA SLEDAI scoring modified to use the SLEDAI-2K scoring for proteinuria. ANA will be collected at screening and baseline only. Other autoantibodies will be collected from all patients at baseline, then at regular intervals in patients positive at baseline.

#### **Renal Flare Definition:**

The following is the definition of *renal flare* ([Alarcón-Segovia](#) et al, 2003) consisting of the development of one or more of the following 3 factors:

- Increased Proteinuria (using spot urine)  
A reproducible increase in 24-hour urine protein levels to:  
    > 1,000 mg if the baseline value was < 200 mg  
**OR**  
    > 2,000 mg if the baseline value was between 200 and 1000 mg  
**OR**  
More than twice the value at baseline if the baseline value was > 1000 mg
- Impaired Renal Function  
A reproducible decrease in GFR of > 20%, accompanied by proteinuria (> 1000 mg/24 hours), hematuria ( $\geq 4$  RBCs/hpf or above the reference range for the laboratory), and/or cellular (RBC and WBC) casts.
- New Hematuria  
New, reproducible hematuria ( $\geq 11$  to 20 RBCs/hpf) or a reproducible increase in hematuria by 2 grades compared with baseline, associated with > 25% dysmorphic RBCs, glomerular in origin, exclusive of menses, accompanied by either an 800 mg increase in 24-hour urinary protein levels or new RBC casts.

#### **8.5.5. Secondary Efficacy Analyses**

The SRI response rate with the SELENA SLEDAI scoring for proteinuria at Week 52 will be compared between the belimumab treatment group and the placebo group using the same analysis methods as described for the primary endpoint in Section [8.5.2](#).

The time to the 1st severe SLE flare over 52 weeks will be compared between the belimumab treatment group and the placebo group using the Cox proportional hazard model. The independent variables in the model will include treatment groups (ie, belimumab vs placebo), baseline SELENA SLEDAI score ( $\leq 9$  vs  $\geq 10$ ), complement level (C3 and/or C4 low vs other), and region (US/Canada vs rest of the world). However, the adjustment will not occur for any of these baseline randomization factors that has < 10 events (ie, severe flares) or < 10 non-events in a stratification level. If a subject withdraws from the study or completes the study up to the Day 364 (Week 52) visit without any severe SLE flare, time to the 1st severe SLE flare will be censored at the time of the last observation. If a subject receives a dose of protocol prohibited/restricted medication that results in treatment failure designation up to the Week 52 visit, the subject will be considered as having a severe SLE flare at the time the medication is started.

The percent of subjects with average prednisone dose that has been reduced by  $\geq 25\%$  from baseline to  $\leq 7.5$  mg/day during Weeks 40 through 52 will be compared between the belimumab treatment and the placebo groups using a logistic regression model. The independent variables in the model will include treatment groups (ie, belimumab vs placebo), baseline SELENA SLEDAI score ( $\leq 9$  vs  $\geq 10$ ), complement level (C3 and/or C4 low vs other), and region (US/Canada vs rest of the world). However, the adjustment

will not occur for any of these baseline randomization factors that has < 10 events (ie, having a prednisone reduction by  $\geq 25\%$  from baseline to  $\leq 7.5$  mg/day during Weeks 40 through 52) or < 10 non-events in a stratification level. The analysis will be performed on subjects who used prednisone  $> 7.5$  mg/day at baseline. Any subject who withdraws from the study prior to the Day 364 (Week 52) visit, misses the Day 364 (Week 52) visit, and/or receives a dose of protocol prohibited/restricted medication that results in treatment failure designation prior to the Day 364 (Week 52) visit will be considered as without any prednisone reduction for the analysis.

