#### **5.5.1.2. Corticosteroids**

In this section, total systemic steroid dose is defined as the average daily dose of all steroids taken SC, IV, IM, intradermally, and orally for both SLE and non-SLE reasons. At baseline, the average daily dose of steroids is the sum of steroid dose over 7 consecutive days up to, but not including Day 0, divided by 7. While on treatment, the average daily dose of steroids is the sum of steroid dose over any 7 consecutive days divided by 7 in the respective time window.

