**5.5.1.2.4. Tapering or Restoration/Restart of Steroids**

The primary objective of this trial is to evaluate the ability of belimumab to reduce SLE disease activity. Premature or rapid reduction in steroids may confound interpretation of study results and could induce a flare. However, it is understood that an important goal of therapy is to reduce steroids, given their associated morbidity. As such, subjects who have improving SLE disease activity for at least 8 weeks may, at the investigator's discretion, reduce the steroid dose targeting a reduction to 7.5 mg/day or lower after the Day 168 (Week 24) visit. Investigators should consider the guidance provided in [Table 5-1](#) below. This table reflects the ACR draft guidance regarding steroid reduction during periods of stable SLE disease. If the subject continues to have stable or improving disease activity after 4 weeks on a reduced dose, then the investigator may consider reducing the dose again. During attempts to wean subjects from steroid use altogether, alternating

dosages (eg, alternating 6/3/6 mg/day) are permitted to help guard against Addisonian crises. Caution should be exercised when discontinuing steroids before the Day 364/Exit (Week 52) visit, given the potential to induce a flare and thereby confound the study results.

If a subject has had worsening SLE disease activity, then a 12-week period of stable or improving disease activity should be observed before considering a clinically significant steroid dose reduction. (Note: The investigator may always apply their clinical judgment as to whether a dose reduction is appropriate.)

Subjects who have their prednisone or equivalent tapered may have their dose increased up to the maximum allowed as defined in Section 5.5.1.2.1 and Section 5.5.1.2.3 (see [Appendix 6](#)).

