**Table 5-1 Algorithm for reducing dose of prednisone**

Daily Dose (mg)	Dose Reduction (mg)
Up to 7.5	1.0
> 7.5 to 15	2.5
> 15 to 30	5.0
> 30 to 40	10.0
> 40	Taper at the investigator's discretion using draft guidelines prepared for ACR (see Appendix 6 )

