### **8.5.3. Secondary Efficacy Endpoints**

The major secondary efficacy endpoints include:

1. SRI response rate with the SELENA SLEDAI for scoring of proteinuria at Week 52.
2. Time to first severe flare (as measured by the modified SLE Flare Index; with SLEDAI-2K and SELENA SLEDAI as the SLEDAI criterion of the SFI).
3. Percent of subjects whose average prednisone dose has been reduced by  $\geq 25\%$  from baseline to  $\leq 7.5$  mg/day during Weeks 40 through 52, in subjects receiving greater than 7.5 mg/day at baseline.

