### **8.5.6. Other Efficacy Analyses**

The analysis of all other efficacy endpoints will be described in the statistical analysis plan.

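### The logistic model for the steroid-reduction endpoint omits baseline prednisone dose, which sets how large a cut each subject needs; adding it is a small, cheap efficiency gain

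*Protocol*

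**What the plan says.** Section 8.5.3 defines major secondary endpoint 3 as the "Percent of subjects whose average prednisone dose has been reduced by" at least 25% from baseline, to 7.5 mg/day or less, during Weeks 40 through 52. Section 8.5.5 restricts the analysis set ("The analysis will be performed on subjects who used prednisone" above 7.5 mg/day at baseline) and states that the proportions "will be compared between the belimumab treatment and the placebo groups using a logistic regression model". The listed terms are treatment, baseline SELENA SLEDAI (9 or less versus 10 or more), complement level and region. Adjustment "will not occur for any of these baseline randomization factors that has < 10 events" or fewer than 10 non-events in a level. Withdrawal, a missed Week 52 visit and treatment failure all count as no reduction. The Synopsis repeats this model.

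Section 8.5.6 hands on only the remaining endpoints: "The analysis of all other efficacy endpoints will be described in the statistical analysis plan". The model for endpoint 3 is therefore set in the protocol itself.

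Baseline dose is already defined. Under Section 5.5.1.2, "the average daily dose of steroids is the sum of steroid dose over 7 consecutive days up to, but not including Day 0"; that weekly total is then averaged per day. Section 4.1, criterion 6, allows entry on up to 40 mg/day.

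**The concern.** The analysis set runs from just above 7.5 to 40 mg/day, and success requires both a relative cut and one absolute level that is the same for everyone. Two subjects in this analysis can therefore face very different tasks, and baseline dose determines the difference. None of the model's covariates carries that information. Dose is not a randomization stratum either, so chance imbalance between arms would go unadjusted. The subgroup cut at 7.5 mg/day in Section 8.5.2.1 does not help, because every subject here lies above it.

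Randomization protects the type I error, so validity is not at stake. What is at stake is precision, in an endpoint analysed only in part of the roughly 501 subjects and for which the protocol states no power.

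**Working it through.** **1. The protocol's own power figures.** With 334 versus 167 subjects and a two-sided 5% test with pooled variance, 59.50% versus 43.95% gives 91.0% power (stated: at least 90%), and 58.2% versus 44.8% gives 81.1% (stated: approximately 80%). Both reproduce. They concern the two SRI endpoints only; nothing comparable is given for the steroid endpoint.

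**2. Cut needed for success.** From Section 8.5.3, required cut = max(25%, 1 − 7.5/baseline dose).

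| Baseline (mg/day) | Cut needed |
|---|---|
| up to 10 | 25% |
| 12.5 | 1 − 7.5/12.5 = 40% |
| 15 | 50% |
| 20 | 62.5% |
| 25 | 70% |
| 30 | 75% |
| 40 | 81.25% |

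This follows from the definition alone and needs no assumption about tapering.

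**3. Direction from the taper guidance.** Section 5.5.1.2.4 lets investigators "reduce the steroid dose targeting a reduction to 7.5 mg/day or lower after the Day 168 (Week 24) visit", the same target whatever the starting dose. With the Table 5-1 steps, 10 mg/day reaches 7.5 in 1 step. From 40 mg/day it takes 7: 30, 25, 20, 15, 12.5, 10, 7.5. The guidance is discretionary, so this supports the direction of a dose effect but not its strength.

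**4. Simulation inputs, all assumed.** The protocol gives no subset size, dose mix, event rate, effect or prognostic strength for this endpoint.
- Subset n = 150, 200 or 300; 2:1 allocation.
- Two dose mixes. Mix A: 10 mg 35%, 12.5 mg 7%, 15 mg 15%, 20 mg 20%, 25 mg 6%, 30 mg 9%, 35 mg 2%, 40 mg 6%. Mix B: equal shares.
- Conditional odds ratio 1.0, 1.5 or 2.0. The smaller effect is included because Section 1.3.4 reports that Phase 3 steroid reductions favoured 1 mg/kg.
- Four prognostic strengths, linear in log dose on the logit scale.
- Three randomization factors (65/45/45%) with the fewer-than-10 rule applied; Wald test at two-sided 5%; 4000 trials per cell.

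**5. Change in power from adding log dose (percentage points).**

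| Placebo success at 10 / 40 mg | OR 1.5 | OR 2.0 | Largest simulation SE |
|---|---|---|---|
| None: 22% / 22% | −0.2 to +0.5 across both ORs | | 0.25 |
| Weak: 25% / 18% | −0.1 to +0.4 across both ORs | | 0.29 |
| Moderate: 30% / 7% | +0.6 to +1.2 | +1.9 to +2.7 | 0.46 |
| Strong: 35% / 1.5% | +0.9 to +2.8 | +4.0 to +7.8 | 0.58 |

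Nothing in the protocol supports the strong gradient; it is an upper bound.

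**6. Validity and estimation.**
- Type I error: 3.7–5.5% without dose, 4.4–5.5% with it.
- The standard error of the log odds ratio rises with dose in the model: 0.3–1.1% (none or weak), 2.3–3.9% (moderate, for example 0.293 to 0.302) and 7.5–10.9% (strong). The odds ratio becomes conditional on dose and moves further from 1: for a true conditional value of 2.0 in the moderate case, the median is 1.95–1.99 without dose and 2.03–2.07 with it.
- The standardised risk difference is the same from both models (for example 12.8 points). In the moderate case its 95% interval is 1.7–3.1% narrower, for example 20.4 to 19.9 points wide. With no or weak prognosis, the variance ratio (without/with dose) is 0.99–1.00, so there is no gain.

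**7. Cross-check with other inputs.** A separate simulation used n = 200 or 300, placebo success 12%, OR 2.3, different dose mixes, no randomization factors and 1000 runs per scenario. Power changed by about 0 with no dose effect, 0 to +1 points at −0.5 log-odds per doubling of dose, 0 to +2 at −1.0 and +3 to +6 at −1.5. Type I error was 3.4–5.7% across both models.

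**The case against.** The strongest reply is that nothing here is wrong. The model is prespecified, uses the same covariates as the primary and severe-flare analyses, and controls the type I error. No power is claimed for this endpoint, so no commitment is missed. All of that stands.

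Second, the gain is unquantified. A required cut is not a probability of success, Table 5-1 takes larger steps at higher doses, tapering is at the investigator's discretion, and withdrawal, missed visits and treatment failure also produce failures. That stands too: strength is unknown, and only the direction is well supported. At OR 1.5 in the moderate case, the low end of the gain (+0.6, simulation SE up to 0.46) is not clearly above zero. The moderate gradient is about −0.87 log-odds per doubling, and the cross-check at a steeper −1.0 found only 0 to +2 points.

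Third, there is a price. The odds ratio changes meaning and its standard error rises. At n = 150 with 22% success there would be about 150 × 0.22 = 33 events for five terms, or 6.6 per term. The simulations at n = 150 nonetheless show no inflation of type I error, and the largest power loss in any cell is 0.2 points (simulation SE 0.17).

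Finally, the wording does not strictly forbid further covariates. But it lists the terms, none concerns steroid dose, and only the other endpoints are left to the SAP.

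**Conclusion.** The point holds, as a modest efficiency improvement and not as an error. The protocol fixes a valid model that omits the variable determining each subject's hurdle, from a 25% cut at 10 mg/day to 81.25% at 40 mg/day. If dose is moderately prognostic, including it gains about 1 to 3 points of power and a slightly narrower interval for the standardised risk difference. If dose is weakly or not prognostic, nothing material changes in either direction. These sizes rest on the assumed subset size, dose mix, effect and gradient. The required cuts and the omission itself rest on the protocol alone. No figure stated in the protocol changes.

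**What to change.** Before unblinding, amend the model for major secondary endpoint 3 in Section 8.5.5 and the Synopsis:

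- Add log baseline average daily prednisone dose, as defined in Section 5.5.1.2, as one continuous covariate.
- State that the rule on fewer than 10 events or non-events, written for levels of the randomization factors, does not govern this term.
- State that the resulting odds ratio is conditional on baseline dose.
- Report beside it a standardised (marginal) risk difference with its 95% confidence interval from the same model. The precision gain appears there; the standard error of the odds ratio does not shrink.

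The cost is one parameter, an odds ratio that differs in meaning from the one now planned, and one extra reported estimate. No new data are needed, since baseline dose already selects the subset and enters the endpoint. No dosing or taper rule changes.

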### **8.5.6. Other Efficacy Analyses**

The analysis of all other efficacy endpoints will be described in the statistical analysis plan.

## **8.6. Safety**

### **8.6.1. Definition of Safety Variables**

Safety will be evaluated by adverse events, changes in laboratory parameters, and immunogenicity.

### **8.6.2. Analysis of Safety Variables**

AEs will be graded for severity by the investigator using Adverse Event Severity Grading Tables ([Appendix 12](#)) or the grades in Section [7.7](#), as appropriate. The frequency of AEs will be tabulated by MedDRA system organ class (SOC) and preferred term. Additional analysis may be performed based on event rates adjusting for subject-years on study agent if the dropout rates are unbalanced across treatment groups. AEs will also be summarized by MedDRA SOC and preferred terms for those that are considered to be severe (Grade 3 and Grade 4) and those that are considered serious. Discontinuations due to AEs will be summarized.

The frequency of laboratory abnormalities will be tabulated by treatment group. Laboratory values will be assessed for significant changes from baseline. Laboratory toxicity will be graded using Adverse Event Severity Grading Tables when possible. Shift tables will be used to determine if subjects move from normal to abnormal during the course of the study. Shifts of  $\geq 2$  grades and Grade 3 or 4 laboratory abnormalities will be summarized.

### **Safety Endpoints of Special Interest**

- All cause mortality
- Serious and/or severe infections
- Opportunistic infections
- Malignant neoplasms
- Selected serious psychiatric events
- Suicidality assessment (see [Appendix 3](#) and [Appendix 4](#))

- Infusion/hypersensitivity reactions
- Immunogenicity

The analyses of these safety endpoints will be described in the statistical analysis plan.

## **8.7. Pharmacokinetics**

### **8.7.1. Definition of Pharmacokinetic Evaluation**

All randomized subjects will be sampled for serum belimumab levels. Serum belimumab concentration data will be used in a population PK analysis. Assessment of belimumab concentrations will be performed at the timepoints indicated in [Table 6-1](#).

### **8.7.2. Analysis of Pharmacokinetics**

Serum belimumab concentration will be determined by an electrochemiluminescence (ECL)-based assay. Results for this study will be presented using appropriate graphic and tabular summaries. Serum belimumab concentration data obtained from this study will be used in a population PK analysis, which will be reported separately. Potential effects of demographic and disease characteristics, concurrent medications, or renal function on belimumab PK will be evaluated.

## **9. PHARMACOGENETICS (PGx)**

In consenting subjects, a blood sample for PGx research will be drawn predose, preferably on Day 0, but samples may be drawn at any time while the subject is participating in the study, to better characterize genetic variability (eg, HLA typing) that may affect efficacy or safety endpoints. Information regarding PGx research is included in [Appendix 11](#).

The IEC/IRB and, where required, the applicable regulatory agency must approve the PGx assessments before these can be conducted at the study site. The approval(s) must be in writing and clearly specify approval of the PGx assessments (ie, approval of [Appendix 11](#)). In some cases, approval of the PGx assessments can occur after approval is obtained for the rest of the study. If so, then the written approval will clearly indicate that approval of the PGx assessments is being deferred and the study, except for PGx assessments, can be initiated. When PGx assessments are not approved, then approval for the rest of the study will clearly indicate this and that PGx assessments will not be conducted.

## **10. STUDY ADMINISTRATION**

Belimumab is under joint development by Human Genome Sciences, Inc. and GlaxoSmith Kline Pharmaceuticals. Human Genome Sciences, Inc. is the sponsor of this study.

## **10.1. Informed Consent**

A copy of the proposed informed consent document must be submitted to the sponsor or designee for review and comment prior to submission to the reviewing IRB/IEC. The consent form must be approved by the IRB/IEC and contain all elements required by national, state, local, and institutional regulations or requirements.

It is the responsibility of the investigator to provide each subject with full and adequate verbal and written information using the IRB/IEC approved informed consent document(s), including the objective and procedures of the study and the possible risks involved before inclusion in the study. Each subject must voluntarily provide written informed consent (including consent for the use and disclosure of research-related health information). The consent must be obtained prior to performing any study-related procedures that are not part of normal patient care, including screening and changes in medications including any washout of medications. A copy of the signed informed consent must be given to the study subject.

## **10.2. Institutional Review Board Review/Independent Ethics Committee Review and Approval**

The investigator or sponsor (as appropriate per national regulations) shall assure that an IRB/IEC, constituted in accordance with the ICH Guideline for Good Clinical Practice (GCP), will provide initial and continuing review of the study.

Prior to shipment of the study agent and enrollment of study subjects, documented IRB/IEC approval of the protocol, informed consent form, and any advertisement for subject recruitment must be obtained and provided to the sponsor or designee.

The IRB/IEC must also be informed of all protocol amendments prior to implementation. The investigator must provide reports of any change in research activity (ie, the completion, termination, or discontinuation of a study) to the IRB/IEC.

